3.2.2 Exclusion criteria

- Age < 18 years old
- Bilateral subdural hematomas
- Subdural volume $< 115\text{cc}$
- Acute subdural hematoma
- Patient does not undergo surgical evacuation
- Other evidence of intracranial injury (i.e. epidural hematoma, intraparenchymal hemorrhage, skull fractures, subarachnoid hemorrhage, hydrocephalus)
- Patient's family not available for consent and requires emergent surgical evacuation
- Previous intracranial surgery
- Recent head trauma (< 1 week)

Title: Clinical Action of Curcumin/Turmeric In chronic Subdural hematoma recurrence (CACTIS)

- Use of anti-coagulation (i.e. Coumadin, Heparin, Apixaban, and Rivaroxaban) or anti-platelets (Plavix) drugs, with the exception of Aspirin
- Known coagulopathy disorders
- Positive urine or serum pregnancy test in pre-menopausal female subjects, without a documented history of surgical sterilization; or currently breastfeeding

1.1.1.□.1. Since the nuclear group in an older population, the pregnancy test will be made in exceptional cases.

- Allergy to curcumin or turmeric.
- Allergy to black pepper
- Markwalder Grading Scale

1.1.1.□.1. Score: 3-4

- Baseline dementia (for more than 6 months).
 - Adult who cognitively impaired for more than 6 months will be excluded from the study, since this impairment might be due to other reasons than cSDH, such as dementia or cognitive impairment.

4. Number of Subjects

This is a single center pilot study. A total of 48 subjects will be recruited in this study.

24 patients will receive placebo pills, and 24 will receive Curcumin (CC) pills. Patients will be first stratified according to their pre-surgery hematoma volume. Randomization will be performed within each hematoma volume group (12 subjects per hematoma volume group) to ensure equal distribution between placebo and CC groups.

Study Timelines

- Duration of an individual subject's participation in taking CC or placebo will be for up to a maximum of 60 days, with follow-up at 6 months and 18 months
- Clinical follow-up with CT scans will be up to 6 months, depending on if residual total hematoma volume < 80cc
- Enrollment of subjects will continue for 2 years.
- Complete data analysis will be performed within 2 years.

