Patients who have symptomatic unilateral chronic subdural hematomas, with no acute component and do not meet the exclusion criteria, will be evaluated. At the time of consent for evacuation of the subdural hematoma, patients will also be consented for this trial by the research team. They will be instructed that they will be randomized to either the placebo group or the curcumin group. They will take one capsule three times a day for a maximum of 60 days. They will undergo standard post-operative care in regard to imaging and clinical follow-up.

Evaluation:

1. Patient evaluated by neurosurgery resident

Title: Clinical Action of Curcumin/Turmeric In chronic Subdural hematoma recurrence (CACTIS)

2. Patient or POA consented by Neurosurgery resident for cSDH evacuation in the operating room.
3. Evaluated by research team for inclusion into trial within 48 hours of presentation to the Neurosurgery service
4. Consent patient or POA for trial participation

Interventions:

1. *Intra-operatively*, patient has samples sent to lab
 - a. At least 10 cc of subdural hematoma fluid will be collected during the initial and recurrence operative, along with 5 cc blood from an existing IV
 - b. The SDH fluid and blood samples will be sent to [name] lab and used in the experimental setup within 10-15 days of collection and in addition analyzed for inflammatory cytokines/chemokines.
2. *Presurgical randomization by stratified hematoma volume.* Presurgical hematoma volume randomization is important because recurrence of cSDH has been shown to be related to presurgical hematoma volume by Stanisic et al.³⁷ The hematoma volume and other CT characteristics are recorded as shown in **Table 1** below.
 - a. Hematoma volume will be recorded and stratified into two groups according to hematoma volume: >140 ml and \leq 140 ml. The process of stratification and subsequent randomization will be done by the IDS pharmacist who will conceal the randomization results from all study team members until after the results of the study have been analyzed.
 - b. After the first patient is consented, we will record his or her hematoma cavity volume. All subjects will be assigned to a treatment group to receive either curcumin-containing or non-curcumin-containing capsules.

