 - c. For the next patient, we will first determine the hematoma cavity volume group; this patient's Tx assignment (CC or placebo) will be alternate to the immediately preceding patient. This process is repeated until all of the patients are enrolled.
3. The patients will start medication **within 24 hours after surgery**, or as soon as they are able to take oral medication
 - a. 1 capsule three times a day (with breakfast, lunch, and dinner) for a maximum of 60 days or until resolution of subdural hematoma
 - b. Resolution will be defined as residual total hematoma cavity volume $<$ 80cc
 - i. If the post-subdural drain removal scan demonstrates a residual total hematoma volume $<$ 80cc, the patient will not be included in the study sample; although, the patient may receive more than one dose of CC by the time of the CT scan.

- CT Imaging:
 - Pre-operative CT SOC scan-- If the hematoma volume is $<$ 115 cc, the patient will not be included in the study
 - Post-operative day one CT SOC scan
 - Post subdural drain removal SOC scan--If the residual total hematoma cavity volume is $<$ 80cc, the patient will be removed from study, as the curcumin has not had time to influence the patient's reabsorption.
 - During the SOC 1 week follow-up appointment, the attending will decide on the need for a repeat CT scan in 4 weeks based on the patient's **post-subdural drain removal SOC scan**. The considerations for re-evacuation include: lack of resolution of the initial clot, an obvious increase in size of the clot, persistent headache, onset of seizures, or onset of new deficit or headache. These criteria will be used in all subsequent considerations for surgical re-evacuation.

Title: Clinical Action of Curcumin/Turmeric In chronic Subdural hematoma recurrence (CACTIS)

- If the residual total hematoma volume is $\geq 80\text{cc}$, the patient will receive an additional CT scan (SOC) for an appointment one month following the previous appointment (Approximately post-operative day 37)
- If there is a decline in neurological exam or other clinical concern, the neurosurgeon may perform an earlier CT scan
- This will continue on a monthly basis for 6 months, or until residual total hematoma cavity volume is $< 80\text{cc}$
 - **Resolution** will be defined as residual total hematoma cavity volume $< 80\text{cc}$
 - Patients with resolution of their hemorrhage will no longer require follow-up visits. Their pills will be returned and discarded.

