This is a **pilot study** aiming to establish potential effect of CC on hematoma volume change as well as measurements and criteria for surgical intervention and cSDH recurrence. The sample size of 25 for each group is determined based on the patient population size and logistics of recruitment and will not reach the conventional statistical power of 80% or more unless the resolution rate of cSDH is 50% greater in CC than in placebo. To establish the effect size, we will compare CC and placebo groups by performing specific statistical analysis for each primary and secondary outcome: linear-mixed effects models for the trajectory hematoma volume over the period of up to six month (change and rate of change); survival analysis for time-to-resolution (since patients will be "censored" in their follow-up); Fisher's exact test and logistic regression for rate of surgical intervention or recurrence (criteria to be developed) as well as the rates of exiting symptoms removal and new symptom occurrence. These analyses serve multiple purposes: establish CC effects compared to the placebo; identify determinants of the various endpoints, and pilot-test working definition of recurrence etc. We will also report descriptive statistics and estimation, using confidence interval of 75% (instead of 95% used for large trials). The confidence interval will be interpreted with regards to the minimum clinically important difference (MCID). [name], PhD and Professor at the Division of Epidemiology, Biostatistics, and Preventive Medicine, Director of UNM CTSC Biostatistics, Epidemiology and Research Design Core, will serve as a co-investigator and oversee the statistical analysis and data interpretation. k

B. Laboratory Studies.

Experimental data on endothelial cell permeability after exposure to cSDH fluid at different concentrations of CC and the changes in protein expression will be quantified using Prism and GraphPad Prism software. Group comparisons using two-way analysis of variance (ANOVA) followed by Tukey's multiple comparison test will be performed to detect significance of differences between control (no treatment), IL-8-treated, IL-8/CC-treated, cSDH fluid-treated, and cSDH-fluid/CC-treated samples. For more detailed statistical analysis, we will use mixed model repeated measures with Wald tests between groups, followed by Sidak's family-wise error rate correction for multiple comparisons within each experimental group.

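### Allocation is stratified by pre-surgery hematoma volume, but the plan commits no between-arm clinical analysis to that stratum, so precision or power is lost if the stratum is prognostic

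*Combined protocol and SAP*

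**What the plan says.** Section 4 (Number of Subjects): "Patients will be first stratified according to their pre-surgery hematoma volume". It continues: "Randomization will be performed within each hematoma volume group (12 subjects per hematoma volume group".

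Section 9 (Study Procedures), Interventions item 2, sets the cut: "stratified into two groups according to hematoma volume: >140 ml" against 140 ml or less. Its reason is that "recurrence of cSDH has been shown to be related to presurgical hematoma volume". Item 2c then gives the mechanism: after the volume group is determined, the patient's assignment "will be alternate to the immediately preceding patient". It does not say whether that means the preceding patient in the same volume group or the preceding patient overall.

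Section 9 (Data Analysis), A. Clinical Studies, Statistical analysis, lists the between-arm methods: "linear-mixed effects models for the trajectory hematoma volume over the period of up to six month (change and rate of change" for volume, "survival analysis for time-to-resolution", and Fisher's exact test with logistic regression for re-operation, recurrence and symptom rates. Neither the 140 ml stratum nor pre-operative volume is named in any of them. The same paragraph gives finding the determinants of each endpoint as one purpose of the analyses, without naming a factor.

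**The concern.** The design uses volume to balance the arms, and the analysis text does not carry it forward. If the arms are balanced within a prognostic stratum and the analysis ignores it, variation between strata stays in the estimated error of a linear contrast although balancing has removed it from the true sampling error. In Cox and logistic models the main effect of leaving it out is that the estimate is pulled toward no effect.

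This matters because the plan concedes limited power and says its purpose is to establish the effect size, with 75% intervals read against a minimum clinically important difference. The estimate and its interval are therefore the main product of 48 patients. Leaving the choice open also allows adjusted or unadjusted results to be selected after the data are seen.

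**Working it through.** **The plan's own figure.** It says 25 per group reaches 80% power only if the resolution rate is 50% greater on curcumin. This cannot be reproduced uniquely, because the placebo rate, alpha, sidedness and test are missing. With 25 per arm and two-sided 5%, an absolute gain of 50 points gives 97–99% power. A relative gain of 1.5 gives 12.5% at 20% v 30% and 44.5% at 50% v 75%. A hazard ratio (HR) of 1.5 needs 191 events. The present point does not depend on this figure.

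**Inputs.** From the documents: 48 patients, two strata cut at 140 ml, monthly CT for up to six months. Assumed: 12 per arm per stratum (12 × 2 × 2 = 48), exponential resolution times, and the size of the stratum effect.

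**1. Time to resolution.** Unstratified and stratified log-rank tests were simulated at two-sided 5% in two settings.
- Setting A: treatment HR 2.25, median 3 months on placebo midway between strata (log scale), 5,000 runs. This HR would give 80% power if all 48 patients had events: exp[(1.960 + 0.842)/√(48/4)] = 2.25.
- Setting B: treatment HR 2, median 60 days in the smaller-volume placebo stratum, scans from day 37 to day 187, 5,000 runs.

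Power (%) and loss (points) from ignoring the stratum:

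| Stratum HR | A unstrat. | A strat. | Loss | B unstrat. | B strat. | Loss |
|---|---|---|---|---|---|---|
| 1.0 | 73.2 | 72.4 | −0.8 | 62.5 | 60.8 | −1.7 |
| 0.8 | – | – | – | 61.4 | 60.0 | −1.4 |
| 0.67 | 71.3 | 72.1 | 0.8 | 58.4 | 59.4 | 1.0 |
| 0.5 | 64.8 | 69.8 | 5.0 | 52.7 | 57.1 | 4.4 |
| 0.33 | 55.9 | 68.3 | 12.4 | 41.5 | 53.9 | 12.4 |

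A separate 3,000-run simulation of setting B gave 52 v 56% at 0.5 and 42 v 53% at 0.33. Simulation error on a single power figure is about √(0.7 × 0.3/5000) = 0.65 point. As a check, setting A had about 41 events at stratum HR 1.0, and Φ(√41/2 × ln 2.25 − 1.96) = Φ(0.64) = 74%, close to the simulated 73.2%.

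Type I error of the unstratified test in setting A was 5.6, 4.8, 4.9 and 3.2% at stratum HR 1.0, 0.67, 0.5 and 0.33. The stratified test gave 5.7, 5.1, 6.2 and 5.4%.

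**2. Volume level or a single time point.** If the stratum explains a share R² of outcome variance, the ratio of unadjusted to adjusted standard error is about 1/√(1 − R²). This gives 1.026, 1.054, 1.118 and 1.195 at R² of 5, 10, 20 and 30%. A version with degree-of-freedom terms for n = 48, √{[(45/46)(1 − R²) + (48/46)R²]/(1 − R²)}, gives 1.016, 1.046, 1.113 and 1.194. The two differ by at most one percentage point. With balance within strata, a nominal 75% interval covers 2Φ(1.15/√(1 − R²)) − 1, which is 77.5% at R² = 10% and 81.6% at 25%.

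**3. Rate of change.** A stratum shift in level cancels out of each patient's slope. In a small mixed-model simulation (60 runs per scenario), a level-only stratum effect moved the standard error of the arm difference in level from 5.94 adjusted to 6.58 unadjusted. The arm-by-time slope was unaffected (1.37 v 1.36). When the stratum also changed the slope, the slope standard error was 1.34 adjusted and 1.47 unadjusted.

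**4. If alternation ignores stratum.** Rerunning setting A that way, the unstratified test kept a type I error of 4.8–5.8%. Power was still lost: 64.7 v 69.2% at stratum HR 0.5 and 55.7 v 67.3% at 0.33.

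**The case against.** The strongest reply is that the text is silent rather than opposed. It specifies no covariates for any model and names no survival method, and its aim of finding determinants implies covariates somewhere. That stands to this extent: the plan does not say, and it should not be read as having decided against adjustment. But looking for determinants is a separate purpose that does not bind the curcumin-versus-placebo comparisons, and Fisher's exact test on a two-by-two table cannot carry a stratum.

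Second, evidence for a strong stratum effect is thin. The stated premise concerns recurrence, not speed of resolution or trajectory. The Background reports a 115 cc cut, and every enrolled patient is already at or above it. Removing patients whose volume is below 80 cc after drain removal may narrow the contrast further. This stands, so the loss is conditional and could be nil.

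Third, part of the gain at stratum HR 0.5 may be size, since the stratified test ran at 6.2% there against 4.9% unstratified. This also stands, and the 4–5 points should be read with that in mind.

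Fourth, at the 15.65% recurrence rate in the protocol's own unilateral series, 48 × 0.1565 ≈ 7.5 recurrences are expected, so stratifying that comparison gains little. This is accepted.

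A reader might go further and infer that standard errors are too wide in every listed analysis and that no reported interval or p-value has its nominal level. The documents do not support that. It fails for the slope when the stratum affects level only, and it fails throughout if alternation ignores stratum. In Cox and logistic models the loss is mainly attenuation of the estimate. At stratum HR 0.5 or weaker the unstratified log-rank size stayed near 5%.

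**Conclusion.** The omission is certain: allocation is stratified on a factor that the protocol calls prognostic, and no between-arm clinical analysis is tied to it. The consequence is conditional on that factor also predicting trajectory and resolution. Log-rank power loss is about 0–1 point at stratum HR 0.67–1.0, 4–5 at 0.5 and 11–12 at 0.33. The standard error of a level contrast is about 2–19% larger at R² of 5–30%, and the slope contrast is affected only if the stratum changes the slope.

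The direction is conservative, with no false-positive inflation from ignoring the stratum. If alternation runs across strata, standard errors are not overstated, but power is still lost. These sizes rest on assumed stratum effects, assumed medians and equal arms within strata, none of which the documents establish. This is a modest, inexpensive improvement to a pilot, not a flaw that invalidates its results.

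**What to change.** Add to the Statistical analysis paragraph that the primary between-arm analyses carry the allocation stratum (above 140 ml, or 140 ml or less), as follows:

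- **Volume trajectory:** stratum and stratum-by-time as fixed effects in the linear mixed model. A main effect alone does not address rate of change.
- **Time to resolution:** a stratified log-rank test and a stratified Cox model.
- **Recurrence, re-operation and symptom rates:** stratum-adjusted logistic regression, or a Mantel-Haenszel/exact stratified comparison. Expect little gain where events are few.

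State as well whether alternation runs within each volume group or across all patients, because that decides whether unadjusted standard errors would be overstated.

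The cost is one sentence and one or two degrees of freedom, and the stratum is already recorded for every patient. If it proves unrelated to outcome, the simulations put the price at a point or two of power at most (0.8 in setting A and 1.7 in setting B).

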Black pepper/piperine is listed under the FDA as being safe (Appendix 2).²³ The average amount of pepper consumed by a person during a day in the United States is 359 mg, which translates to 18-32 mg of piperine a day. Furthermore, rat trials show a daily intake of 5 to 20 times the average daily dose of humans produced no clinical symptoms. Furthermore, studies on acute, subacute, and chronic piperine toxicity show no abnormalities or clinical symptomatology, or significant blood chemistry data in laboratory animals. Black pepper extract has a high degree of safety being used nutritionally. The amount of piperine that is formulated in the curcumin capsules is several thousand times less than the LD₅₀ established in mice and rats.²² Our capsule contains 270 mg of pure curcuminoids (curcumin) and 3mg of black pepper extract. The recommended serving size is 3 capsules a day. Therefore, the patients will receive 810mg of pure curcumin and **9mg of black pepper extract** (pepperine) per day, which is less than the average amount of pepper consumed by a person daily in the United States.

CT Scans

The use of CT scans to evaluate the volume of hemorrhage in cSDH patients is the standard of care. At our institution, it is standard practice to obtain a minimum of three CT scans over the course of surgical management of a cSDH. The **first CT scan** is obtained pre-operatively to characterize the subdural and determine subsequent management. In patients who receive surgical evacuation, a **post-operative scan (second scan)** is performed to demonstrate adequate drainage of the fluid, improvement in midline shift, and to assess for new hemorrhages or strokes. If a subdural drain is placed intra-operatively, a **third scan** is obtained within 24-hours of subdural drain removal. One study on acute subdural hematomas (aSDH) reported an average of 4.3 CT studies per patient during their hospital stay.³⁴ There is extensive empirical evidence that strongly supports the correlation between pre-operative imaging and pre-and post-operative neurological data and the risk of rebleeding regardless of drain placement and removal.^{12,26,27,33,41} Most researchers agree that the drain removal procedure is risky, but there is no clear consensus on what exactly defines this risk; therefore, a post-operative scan is felt to be advantageous to document the formation of new hemorrhage, hemorrhage as fragile brain tissue and vasculature may be disturbed.^{4,33}

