Utilizing Stanisic et.al findings, our protocol will only include patients with a pre-operative hematoma volume of **115cc** or greater. Similar to this group, we will perform monthly interval CT scans until the total hematoma volume is measured to be less than **80cc**³⁷ our working definition of resolution. At this point, we will determine that the patient has met criteria for **resolution** of the cSDH and would not require further imaging. If the patient demonstrates a neurological change or increased volume, an earlier CT scan will be performed, regardless of volume size.

Conclusion

The current literature and our own preliminary data have demonstrated that there is local elevation of pro-inflammatory chemokines and pro-angiogenic factors within the subdural hematoma cavity of chronic subdural hematomas that are not found systemically. CXCL8 (IL-8) demonstrates both pro-inflammatory and pro-angiogenic properties. Curcumin has shown to directly inhibit the production and activity of CXCL8 (IL-8) *in vitro* and *in vivo*, as well as down regulating the activity of VEGF and bFGF. These combined effects make CC an important anti-inflammatory and anti-angiogenic molecule that has the potential to reduce the recurrence rate of chronic subdural hematomas. We expect that CC will prevent/reduce persistent hemorrhage within the subdural hematoma cavity, by blocking IL-8-induced disruption of the blood vessels. Specifically, CC is expected to preserve blood vessel leakage and accumulation of blood in SDH cavity, by blocking destructive effect of IL-8 on the vascular endothelial tight junctions.

3. Study Design

This is a *double-blinded, randomized placebo-controlled pilot study*. The patients, neurosurgeons, nurses and clinical coordinators will be blinded except for the research pharmacists who will keep a key linking a code # on a bottle handed to the clinical coordinator and the patient's MRN #. The pill bottles handed to the clinical coordinator will be identical for placebo and CC.

Study Type: Interventional

Study Design: Randomized Treatment assignment

Intervention Model: Parallel Assignment

Masking: Double Blind (Subject, Investigators, coordinators, nurses)

Primary Purpose: Treatment

Intervention:

1) Curcumin (turmeric extract), over the counter supplement (1 capsule/three times a day).

Producer Company: Oregon Wild Harvest

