- a. For patients with a residual total hematoma cavity volume $\geq 80\text{cc}$, the neurosurgery attending will determine if the patient requires surgical re-evacuation for a 1 month follow-up in clinic with a repeat Head CT. The considerations for re-evacuation include: lack of resolution of the initial clot, an obvious increase in size of the clot, persistent headache, onset of seizures, or onset of new deficit or headache. These criteria will be used in all subsequent considerations for surgical re-evacuation.
- ii. If there is a decline in neurological exam or other clinical concern, the neurosurgeon may perform an earlier CT scan. The patient will continue to take the placebo or CC three times a day.
3. Patients presenting for their 2nd clinic appointment (Approximately post-operative day #37):
 - a. Repeat CT scan will be performed on the day or near the day of the appointment
 - b. Subdural thickness measurements of remaining subdural fluid will be completed
 - i. Patients with a residual total hematoma cavity volume $< 80\text{cc}$ will be instructed to discontinue the pills. Unused medication will be retrieved from the patients and returned to IDS for destruction. They will not have additional neurosurgical imaging or follow-up required, unless deemed necessary by the neurosurgery attending.
 1. They will continue to be followed by the study team with a 6 month and 18-month phone call
 - ii. For patients with a residual total hematoma cavity volume $\geq 80\text{cc}$, the neurosurgery attending will determine if the patient requires surgical re-evacuation as previously described for a 1 month follow-up in clinic with a repeat Head CT. If there is a decline in neurological exam or other clinical concern, the neurosurgeon may perform an earlier CT scan. The patient will continue to take the placebo or CC three times a day.
 4. Patients presenting for their 3rd clinic appointment (Approximately post-operative day #67):
 - a. Repeat CT scan will be performed on the day or near the day of the appointment
 - b. Subdural thickness measurements of remaining subdural fluid will be completed
 - i. Patients with a residual total hematoma cavity volume $< 80\text{cc}$ will be instructed to discontinue the pills. Unused medication will be retrieved from the patients and returned to IDS for destruction. They will not have additional neurosurgical imaging or follow-up required, unless deemed necessary by the neurosurgery attending.

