 1. They will continue to be followed by the study team with a 6 month and 18-month phone call
 - For patients with a residual total hematoma cavity volume $\geq 80\text{cc}$, the neurosurgery attending will determine if the patient requires surgical re-evacuation as previously described for a 1 month follow-up in clinic with a repeat Head CT. If there is a decline in neurological exam or other clinical concern, the neurosurgeon may perform an earlier CT scan.
 5. Patients will not take CC pills or placebo longer than 60 days. If there are extra pills, they will be properly retrieved and returned to IDS for destruction.

All radiographic imaging discussed here is our institution's standard of care for the management of SDH. If a patient is discontinued, they will still be followed by the research team until the end of the trial (see below).

Follow-up outcome assessments (Modified Ranking Scale (MRS); Markwalder Grading Scale, [MGS]) will be obtained 1 month, 6 months, and 18 months following surgery for research. All data are coded

Title: Clinical Action of Curcumin/Turmeric In chronic Subdural hematoma recurrence (CACTIS)

with a unique identifying number to maintain confidentiality. This exam assesses the patient's neurological status to predict additional progress and evaluate functional status. This exam will be conducted with the use of a structured interview (see attached MRS questionnaire) by phone or in person if the patient has a scheduled appointment by one of the researchers.

[figure not shown]
- Study Follow-Up Phone Calls
 - 1 month, 6 months, 18 months
 - Modified Rankin Scale (MRS)
 - Markwalder Grading Scale

Modified Rankin Scale (mRS)

Score	Degree of Disability
0	No symptoms
1	No significant disability. Able to carry out all usual activities, despite some symptoms
2	Slight disability. Able to look after own affairs without assistance, but unable to carry out all previous activities.
3	Moderate disability. Requires some help, but able to walk unassisted.
4	Moderate severe disability. Unable to attend to own bodily needs without assistance, and unable to walk unassisted.
5	Severe disability. Requires constant nursing care and attention, bedridden, incontinent.
6	Dead.

Markwalder Grading Scale

Mental Status	Neurologic Findings	Grade
normal	Normal	0
fully alert and conscious; may have mild symptoms such as headache	none or mild (reflex asymmetry – i.e. Pronator Drift)	1

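### The time-to-resolution analysis has no rule for re-evacuated patients, so on a literal reading a fall below 80 cc after a second operation counts as resolution

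*Combined protocol and SAP*

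**What the plan says.** Time-to-resolution is one of three primary outcomes in section 5 (Study Endpoints), beside change and rate of change in volume. The Statistical analysis paragraph under Data Analysis, A. Clinical Studies gives its method as "survival analysis for time-to-resolution (since patients will be 'censored' in their follow-up". It gives no reason or time point for censoring.

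The event is defined by volume alone. Study Procedures, Interventions item 3b, begins "Resolution will be defined as residual total hematoma cavity volume" and sets the limit at below 80 cc. The CT list under Study Timelines repeats this, and the CT Scans part of the Background calls it "our working definition of resolution". None of these says how the volume must have fallen.

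Re-evacuation is possible throughout the same follow-up. The CT Imaging list in Study Procedures states: "The considerations for re-evacuation include: lack of resolution of the initial clot, an obvious increase in size of the clot", followed by headache, seizures and new deficits. Under Clinic Follow-up, for patients at or above 80 cc at the one-week visit, "the neurosurgery attending will determine if the patient requires surgical re-evacuation for a 1 month follow-up in clinic with a repeat Head CT". At the second and third visits, "the neurosurgery attending will determine if the patient requires surgical re-evacuation as previously described". Second operations are expected, since "subdural hematoma fluid will be collected during the initial and recurrence operative" (Interventions item 1a).

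Re-operation is otherwise a secondary outcome: its rate is compared by arm with Fisher's exact test and logistic regression, and the physician's reasons are recorded. No text links it to the time-to-resolution analysis.

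**The concern.** Re-evacuation depends on the outcome: not having resolved is one of the listed considerations for it. If the second operation takes the cavity below 80 cc, the volume-only definition is met, and a patient whose treatment failed is scored as a success. The central hypothesis is that curcumin prevents re-accumulation. If that is true, placebo patients have more second operations and gain more surgically produced resolutions, so the primary contrast understates the benefit. If curcumin had more re-operations, the benefit would be overstated.

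Censoring these patients at re-evacuation does not repair this. They are removed partly because they are not resolving, so those who remain are not representative of them.

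The secondary comparison would show an imbalance in re-operation but would not correct the primary estimate. That estimate matters because Objective 1 expects the pilot to support a larger trial.

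**Working it through.** **No plan figure to reproduce.** The point is an omission. The nearest figure, 80% power only if the resolution rate is 50% greater on curcumin, comes without a placebo rate or a scale, so it cannot supply the resolution rates needed here. They are assumed.

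**Inputs**
- *r*, resolution by 6 months without re-operation: 50% placebo, 70% curcumin (assumed).
- *s*, re-operation: 15.65% placebo, the institution's unilateral recurrence rate (Background), used as a proxy. Curcumin 7.8%, about half (assumed). The literature range for recurrence in the Background is 2.3% to 33%.
- *f*, share of re-operated cavities that fall below 80 cc: not in the documents, so varied.
- *n* = 24 per arm (section 4; the Statistical analysis paragraph says 25).

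**Formula.** Apparent resolution per arm = r + f × s. This assumes that re-operated patients would not otherwise have resolved. The apparent difference is (70 − 50) + f × (s on curcumin − s on placebo).

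For 15.65% versus 7.8%, this is 20 − 7.85 × f. Results in percentage points:

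| Re-operation, placebo vs curcumin | f = 0.25 | f = 0.5 | f = 1 |
|---|---|---|---|
| 15.65% vs 7.8% | 18.0 | 16.1 | 12.15 |
| 2.3% vs 0% | 19.4 | 18.85 | 17.7 |
| 33% vs 16.5% | 15.9 | 11.75 | 3.5 |
| equal rates | 20 | 20 | 20 |
| 7.8% vs 15.65% (reversed) | 22.0 | 23.9 | 27.85 |

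If non-surgical resolution were the same in both arms, the first row would show 2.0, 3.9 and 7.85 points in favour of placebo.

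Equal rates leave the absolute difference alone but shrink a ratio. With 15.65% in both arms, 70/50 = 1.40 becomes 77.825/57.825 = 1.35 at f = 0.5 and 85.65/65.65 = 1.30 at f = 1.

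**Patients involved.** 24 × 0.1565 = 3.8 on placebo and 24 × 0.078 = 1.9 on curcumin.

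**Sampling error.** The standard error of 50% versus 70% at 24 per arm is √[(0.50 × 0.50 + 0.70 × 0.30)/24] = √(0.46/24) = 0.138, or 13.8 points. The plan's 75% interval is then about ±1.15 × 13.8 = ±15.9 points. The first-row shifts of 2.0, 3.9 and 7.85 points are about 0.14, 0.28 and 0.57 standard errors.

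**If re-operated patients were censored instead.** In the limiting case where every re-operation precedes every resolution, one minus Kaplan–Meier tends to r/(1 − s): 50/0.8435 = 59.3% and 70/0.922 = 75.9%, a difference of 16.6 points. If every re-operation follows every resolution, it stays at 20. Censoring therefore changes the answer too, by an amount that depends on timing.

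**The case against.** The strongest reply is that the documents are silent rather than wrong. Nowhere do they say that a fall after re-evacuation counts as resolution; that follows only from applying the definition literally. The one-week visit sentence is garbled and may mean re-evacuation *or* a one-month visit with CT. Re-operated patients might then leave the monthly scans and be among those censored. No study CT is scheduled after a second operation, and the figure in the follow-up section could not be consulted. This stands as a limit on certainty. It does not close the gap, because neither reading gives an analysis rule.

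A high *f* is doubtful. Enrolled patients are those whose first evacuation left at least 80 cc, and the cavity measure includes pneumocephalus. This also stands, and it makes the lower values of *f* the more relevant ones.

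Three stronger readings are tempting but not supported:
- *The event would be dated to the day of the second operation.* The Background says a post-operative scan "is performed to demonstrate adequate drainage of the fluid, improvement in midline shift", but that describes the usual course after evacuation. The documents do not say that such a scan after re-evacuation feeds the endpoint.
- *The plan already contains the matching principle*, because it drops patients below 80 cc after the first operation. Its reason is that curcumin has not had time to act. That reason carries over poorly to a patient re-operated after weeks of treatment.
- *The mixed model is biased unless post-re-evacuation scans are removed.* Whether those scans belong depends on the effect being estimated, and reasonable statisticians differ.

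**Conclusion.** The point holds as an omission with a predictable consequence for time-to-resolution. The event is volume only, re-evacuation is expected and depends on the outcome, and no rule connects the two. If re-operation differs by arm, the contrast is distorted, towards no effect if curcumin reduces re-operation. With equal rates the absolute difference is unchanged.

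On the assumed rates, 20 points becomes about 18 to 16 for *f* of 25–50%, and 12 at the extreme of 100%. These shifts are smaller than one standard error at this sample size. Only the far corner (33% versus 16.5%, every cavity below 80 cc) exceeds it, with a shift of 16.5 points. All of this rests on assumed resolution rates, an assumed halving of re-operation, recurrence as a proxy for re-operation, and six-month proportions rather than a survival estimate.

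A reader might infer that the trial's result would be reversed or made unusable. The documents do not support that: few patients are likely to be affected, and re-operation is reported by arm, so an imbalance could be seen. The change is recommended because it is cheap and should be settled before unblinding.

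**What to change.** Add to the Statistical analysis paragraph, before unblinding:

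1. For analysis, resolution means a cavity volume below 80 cc without prior re-evacuation.
2. In time-to-resolution, re-evacuation is a competing event. Re-operated patients stay in the analysis as non-resolved to 6 months. Report cumulative incidence of resolution by arm, with re-evacuation rates beside it.
3. Censoring means the end of imaging follow-up or loss to follow-up, not re-evacuation.
4. Report the mixed model with and without scans taken after re-evacuation. Which is primary is an estimand choice for the sponsor to fix in advance.

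Other strategies for re-evacuation are defensible; one needs to be named.

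Cost: a few sentences. Re-operation and the reasons for it are already to be recorded; the date should be captured with them. On the illustrative rates with *f* of 25–50%, about 0.9 to 1.9 placebo events (3.76 × f) and 0.5 to 0.9 curcumin events (1.87 × f) would no longer count as resolution. No change to clinical management is proposed.
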